**Baseline Erythropoietin Resistance Index (ERI, U/kg/wk/g/L)**

- Calculated by dividing the standardized prior ESA dose (U/week) at randomization by the baseline estimated dry weight (in kg) and then dividing by the achieved Day 1 Hgb (in g/L).
- Note: the central laboratory Hgb value from Day 1 should be used to calculate ERI, however if this value is missing and there is a corresponding non-missing HemoCue Hgb value available, the Day 1 HemoCue Hgb value will be used.

**rhEPO Hyporesponders**

- A subject will be considered to be a hyporesponder if:
  - ERI  $\geq$  2.0 U/kg/wk/g/L
  - Or
  - Prior ESA dose (U/week) at baseline divided by the baseline estimated dry weight (in kg)  $\geq$  450 U/kg/week

CONFIDENTIAL

204837

**Demographics & Baseline Characteristics**

- Note: an ERI  $\geq 2.0$  U/kg/wk/g/L for epoetin-treated subjects corresponds to an ERI  $\geq 0.008\mu\text{g/kg/wk/g/L}$  for darbepoetin-treated subjects and  $\geq 0.01 \mu\text{g/kg/wk/g/L}$  for methoxy-PEG-epoetin-treated subjects.
- Supportive analyses will be used in the summary of demographics and baseline characteristics and will use the following alternative hyporesponder definitions:
  - 1) an ERI cut-point of  $\geq 1.5$  U/kg/wk/g/L only
  - 2) subjects with prior ESA dose (U/week) at baseline in the top 20th percentile of the randomized study population.

**Baseline Post-Dialysis Body Mass Index (BMI)**Calculated as baseline post-dialysis weight (kg) / [height (m)]**Cardiovascular Risk Score**

A risk score for two-year cardiovascular mortality and morbidity in a hemodialysis population has been developed [Anker, 2016] and will be calculated at baseline for each HD participant.

The following table describes how the published risk score is calculated:

ARO Cardiovascular Morbidity and Mortality Risk Score For Patients on Chronic Hemodialysis			
Parameter (unit) and values	Risk Score Points	Parameter (unit) and values	Risk Score Points
Age [years]		Intradialytic Weight Change [kg]	
$\leq 39$	CCI	$< -2.2$	CCI
40 to 49		$-2.2$ to $< -1.7$	
50 to 59		$-1.7$ to $< -1.2$	
60 to 69		$> -1.2$	
70 to 79		Haemoglobin [g/L]	
$\geq 80$		$< 100$	
Smoking Status:		100 to $< 120$	
Current		$\geq 120$	
Former		Reactive Protein [mg/L]	
Non smoker		$< 2.4$	
CVD history		2.4 to $< 6.8$	
Yes		6.8 to $< 18.0$	
No		$\geq 18.0$	
Pre-dialysis SBP [mmHg]		Serum Albumin [g/L]	
$< 120$		$< 35$	
120 to $< 130$		$\geq 35$	
130 to $< 140$		Creatinine [ $\mu\text{mol/L}$ ]	
140 to $< 160$		$< 436$	
$\geq 160$		436 to $< 542$	
CKD Aetiology:		542 to $< 678$	
Hypertension/vascular		$\geq 678$	
Glomerulonephritis		Calcium [mmol/L]	
Diabetes		$< 2.1$	
Tubulo-interstitial		2.1 to $< 2.6$	
Polycystic Kidney Disease		$\geq 2.6$	
Unknown renal diagnosis		Total Cumulated Risk Points	

It should be noted that creatinine is not routinely collected in this study and will be assumed to be the same in all HD participants (i.e.  $< 436$ , resulting in 3 risk score points).

CONFIDENTIAL

204837

Demographics & Baseline Characteristics

CVD history is defined as having a yes response to any of the following medical history conditions: angina pectoris, myocardial infarction, stroke, coronary artery disease, transient ischaemic attack, heart failure, atrial fibrillation, cardiac arrest, and/or valvular heart disease.
 
Intradialytic weight change will be calculated using the Week -4 post-dialysis weight in kg – the Week -4 pre-dialysis weight in kg.
 
Baseline Hgb categories will be defined based on g/dL units (i.e. <10, 10-<12 and >12) and will use central laboratory Hgb values if available. If a baseline central laboratory Hgb value is not available, a baseline HemoCue Hgb value will be used.
 
Risk score points for CKD aetiology will be determined based on the following approach:
 
 
i. Participants with diabetic renal disease are assigned 4 points
 
ii. All other participants who have hypertensive renal disease are assigned 1 point
 
iii. All other participants who have interstitial nephritis are assigned -1 point
 
iv. All other participants who have a medical history of polycystic kidney, autosomal dominant or do not have any of these medical history terms selected are assigned 0 points
 
 
The overall CV risk score is determined by summing up the individual risk scores for the 11 risk factors.

History of Diabetes

 
• Subjects are considered to have a history of diabetes if they have a yes response to any of the following medical history conditions: diabetes, diabetic autonomic neuropathy, diabetic neuropathy peripheral, diabetic dermopathy, diabetic renal disease, diabetic retinopathy.
 
• If subjects have indicated that they do not have any of the listed diabetic medical history conditions above, they are considered not to have a history of diabetes.
 
• If subjects have not been classified as having or not having a history of diabetes and are missing a response to any of the listed medical history conditions, their diabetes history status will be missing.
 

History of Stroke

 
• Subjects are considered to have a history of stroke if they have a yes response to the stroke medical history condition.
 
• Subjects who have indicated that they do not have a history of stroke will be summarized accordingly.
 
• If a subject is missing a response to the stroke medical history condition, their stroke history status will be missing.
 

History of MI

 
• Subjects are considered to have a history of MI if they have a yes response to either of the following medical history conditions: myocardial infarction, cardiac arrest.
 
• Subjects who have indicated that they do not have a medical history of myocardial infarction or cardiac arrest will be considered not to have a history of MI.
 
• If subjects have not been classified as having or not having a history of MI, and are missing a response to either the myocardial infarction or cardiac arrest medical condition, their MI history status will be missing.
 

History of Cancer

 
• Subjects are considered to have a history of cancer if they have a yes response to either of the following medical history conditions: neoplasm malignant or unknown/unspecified, allogeneic bone marrow transplant.
 
• Subjects who have indicated that they do not have a medical history of neoplasm malignant or unknown/unspecified or allogeneic bone marrow transplant will be considered not to have a history of cancer.
 

**CONFIDENTIAL**

204837

**Demographics & Baseline Characteristics**

- If subjects have not been classified as having or not having a history of cancer and are missing a response to either the neoplasm malignant or unknown/unspecified or allogeneic bone marrow transplant medical condition, their cancer history status will be missing.

**History of Heart Failure**

- Subjects are considered to have a history of heart failure if they have a yes response to any of the following medical history conditions: heart failure, left ventricular systolic dysfunction, left ventricular diastolic dysfunction, pulmonary hypertension.
- Subjects who have indicated that they do not have a medical history of all of the terms listed above will be considered not to have a history of heart failure.
- If subjects have not been classified as having or not having a history of heart failure and are missing a response to any of the medical condition terms listed above, their heart failure history status will be missing.

CONFIDENTIAL

204837

Demographics & Baseline Characteristics
History of Thromboembolic Events

 
Subjects are considered to have a history of thromboembolic events if they have a yes response to any of the following medical history conditions: pulmonary embolism, deep vein thrombosis, retinal vein occlusion, arteriovenous graft thrombosis, arteriovenous fistula thrombosis, central venous catheter thrombosis.
 
Subjects who have indicated that they do not have a medical history of all of the terms listed above will be considered not to have a history of thromboembolic events.
 
If subjects have not been classified as having or not having a history of thromboembolic events and are missing a response to any of the medical condition terms listed above, their thromboembolic event history status will be missing.
 

History of Cardiovascular Disease

 
Subjects are considered to have a history of cardiovascular disease if they have a yes response to any of the following medical history conditions: angina pectoris, myocardial infarction, stroke, coronary artery disease, transient ischaemic attack, heart failure, atrial fibrillation, cardiac arrest, valvular heart disease.
 
Subjects who have indicated that they do not have a medical history of all of the terms listed above will be considered not to have a history of cardiovascular disease.
 
If subjects have not been classified as having or not having a history of cardiovascular disease and are missing a response to any of the medical condition terms listed above, their cardiovascular disease history status will be missing.
 

Baseline Iron Use & Standardized Baseline IV Iron Dose
See Section 14.6.3
Phosphate Binder Use at Randomization

 
Phosphate binder use at randomization will be summarized as follows: 
 
Iron-based phosphate binders
 
Calcium-based phosphate binders
 
Non-calcium and non-iron based phosphate binders
 
No phosphate binder use
 
Subjects will be counted in each applicable group, based on the concomitant medications they are receiving on the day of randomization.
 
 
 

Concomitant Medication Use at Randomization

 
Concomitant medication records on the day of randomization will be used to determine the following classifications of concomitant medication use at randomization: 
 
ACEI/ARB
 
Vitamin D
 
Beta blockers
 
SGLT2i
 
Statin
 
Aspirin
 
Vitamin K
 
Insulin
 
Calcimimetics
 
Diabetic medication
 
 
 

CONFIDENTIAL

204837

**14.6.2.2. Study Treatment Discontinuation and Study Withdrawal**

Study Treatment Discontinuation and Study Withdrawal
Study Treatment Discontinuation

 
Study Treatment Discontinuation Censored Time (days) = Treatment stop date – Treatment start date +1
 
 
If the death date ≤ the treatment stop date + 3 days for a subject, the subject will be censored and will not be counted as an event for treatment discontinuation summaries that exclude subjects who die while on treatment.

 
Time to Study Treatment Discontinuation (days) = Treatment stop date – Treatment start date +1
 

 
Study Treatment Person Years = (Cumulative total of time to study treatment discontinuation for subjects who discontinued study treatment + Cumulative total of study treatment discontinuation censoring time for subjects who did not discontinue study treatment) / 365.25
 

 
Study Treatment Discontinuation Incidence Rate (per 100 person years) = 100* Number of subjects who discontinued study treatment / study treatment person years
 

Study Withdrawal

 
Study Censored Time (days) = Study completion date – Randomization date +1
 

 
Time to Study Withdrawal (days) = Study withdrawal date – Randomization date +1
 

 
Study Person Years = (Cumulative total time to study withdrawal for subjects withdrawing from the study + Cumulative total of study censoring time for subjects who did not withdraw from study) / 365.25
 

 
Study Withdrawal Incidence Rate (per 100 person years) = (100 * Number of subjects who have withdrawn from study) / Stud Person Years
 

**14.6.2.3. Prior and Concomitant Medications**

Prior and Concomitant Medications
Non-randomized ESA use during treatment period

 
Subjects will be considered to have non-randomized ESA use during the treatment period if they have any ESA concomitant medication records with one of the following two reasons for medication: 
 
Non-randomized rhEPO treatment in addition to study treatment
 
Non-randomized rhEPO treatment instead of study treatment during treatment period
 
 
 

Duration of non-randomized ESA use during treatment period

 
If there is only one concomitant medication record of non-randomized ESA use during the treatment period, then: 
 
Duration (days) = earliest of (concomitant medication record end date, last non-zero dose date + 1 day) – latest of (concomitant medication start date, treatment start date) + 1 day
 
 
 
If there are multiple concomitant medication records of non-randomized ESA use during the treatment period, then the duration of non-randomized ESA use will add the durations for all records, subtracting any overlapping days that may exist between the multiple records.
 

CONFIDENTIAL

204837

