7.2.4. Temporary Study Treatment Interruption

Every effort must be made to attend study visits and to continue study treatment; however, the site should contact GSK if a participant cannot return to the site on a temporary basis for any reason, including hospitalization, or in case of any unforeseen issue that prevents a participant from receiving study treatment.

In exceptional circumstances, local standard of care for anemia management during this time may be considered based on consultation with the GSK medical monitor. If any non-study rhEPO or analogs are administered, doses should be recorded in the electronic case report form (eCRF).

Participants should return for study visits and restart administration of study treatment as soon as possible, unless the situation warrants permanent discontinuation of study treatment per Section 8.1.

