**6.2.5. Medical Conditions, Prior and Concomitant Medications**

A summary of medical conditions will be provided by treatment group and overall.

For reporting purposes, medications will be classified as prior (pre-treatment), concomitant (on-treatment), and/or post-treatment using the associated start and stop dates recorded in the eCRF and relative to the first and last dose dates of IP (see Section [14.4.1](#)). Medications will be coded using the GSK Drug coding dictionary (current version at the time of DBR).

The number and percentage of subjects reporting the use of each concomitant medication will be summarized by treatment group and overall, anatomical therapeutic chemical (ATC) Level 1, 2, 3, and Ingredient. Summaries of pre-treatment, on-treatment, and posttreatment medication will be provided separately. See Section [14.4.1](#) for a summary of study phases for concomitant medications.

A listing of all medications taken by subjects, including any which are only prior or post-treatment, will be produced. The relationship between ATC level 1, ingredients and verbatim text for all medications in the study will be listed.

The number and percentage of subjects with any non-randomized ESA use in addition to study treatment during the treatment period (see Section [14.6.2](#)) will be provided by treatment group and overall. Similarly, the number and percentage of subjects with any non-randomized ESA used instead of study treatment during the treatment period (see Section [14.6.2](#)) will be provided by treatment group and overall. Additionally, the duration of the non-randomized ESA use during the treatment period will be summarized

using mean, standard deviation, minimum, P25, median, P75, and maximum by treatment group and overall, as well as by the number and percentage of subjects in the following duration categories: < 5 days,  $\geq 5$  days - < 14 days,  $\geq 14$  days - < 28 days,  $\geq 28$  days.

A listing of prior and concomitant ESA use will be provided with details of the ESA use.

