**Demographics & Baseline Characteristics**

- If the concomitant medication record start date  $\geq$  Randomization date, the duration of the record is 0.
- If the concomitant medication record end date + gap factor  $<$  Week -4 visit date, the duration of the record is 0.
- If the concomitant medication record end date + gap factor  $\geq$  Week -4 visit date, the duration of a record will be calculated as Stop Date – Start Date +1 day, where:
  - Start date will be the latest of (concomitant medication record start date and the Week -4 visit date).
  - Stop date will be the concomitant medication record end date + gap factor.
- If the frequency of the record is 'one time dose', then:
  - If the concomitant medication record start date  $\geq$  Randomization date, the duration of the record is 0.
  - If Week -4 visit date  $\leq$  concomitant medication record start date, then:
    - Frequency (for standardization formula) = 1
    - Duration = 7 days
  - If concomitant medication record start date  $<$  Week -4 visit date, then:
    - Frequency (for standardization formula): 7/ [earliest of (the day before the next sequential prior ESA concomitant medication record start date and the day before randomization) – start date of record + 1 day]
    - If the earliest non-missing date of (the day before the next sequential prior ESA concomitant medication record start date and the day before randomization)  $<$  Week -4 visit date, the duration of the record is 0.
    - If the earliest non-missing date of (the day before the next sequential prior ESA concomitant medication record start date and the day before randomization)  $\geq$  Week -4 visit date, the duration of the record is calculated as Stop Date – Start Date + 1, where:
      - Start date will be the Week -4 visit date.
      - Stop date will be the earliest of (the day before the next sequential prior ESA concomitant medication record start date and the day before randomization)
- The total dose for each prior ESA record will be: Standardized dose\*duration/7days
- A weighted mean will then be used to obtain the prior ESA dose:  
 Mean prior ESA dose = [(ESA total doseRecord 1) + ... + (ESA total doseRecord n)]/[( Randomization Date – Week -4 Visit Date)/7days]

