### 14.6.3. Efficacy

#### 14.6.3.1. Hemoglobin Endpoints

Hemoglobin Values
Central Laboratory and HemoCue Hgb Values

 
When source of Hgb measurement is not specified: 
 
For reporting purposes, central laboratory Hgb values will be used, unless otherwise specified. However, if a central laboratory Hgb value is missing, a corresponding non-missing HemoCue Hgb value will be used. This approach will be used for the primary Hgb analysis.
 
 
 
Some displays may be created for either central laboratory Hgb values only or HemoCue Hgb values only. The central laboratory summary will be considered the primary summary in this case.
 

Evaluable Hemoglobin Values

 
Evaluable Hgb values are on-treatment Hgb values (see Section 14.4.1) that are not taken within the 8 weeks following a red blood cell transfusion, a whole blood transfusion, or a non-randomized ESA treatment which occurs on or after the randomization date.
 
Red blood cell transfusions, whole blood transfusions and non-randomized ESA treatments occurring on or after the randomization date are identified by comparing the start and stop date of the respective transfusion or ESA concomitant medication record to the randomization date.
 

Imputed Hemoglobin Values

 
For each missing value between baseline to Week 52 (inclusive), 200 imputed values will be generated using the multiple imputation method (see Section 7.1.5). The average of these 200 imputed values will be used as the value for this missing value in the summary tables and figures.
 

CONFIDENTIAL

204837

Hemoglobin Values					

 
For primary efficacy Hgb analysis and the corresponding subgroup analyses using all available observed and imputed Hgb values (on and off-treatment), Rubin's rules [Rubin, 1987] will be used to combine results of the imputed datasets using SAS PROC MIANALYZE procedure.
 
					
EP Hemoglobin Value for Primary Hgb Analysis					

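### The duration rule for non-randomized ESA use has no dosing-interval extension and no floor, so the descriptive durations in Tables 1.029 and 1.030 can be too short, zero or negative

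*SAP*

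**What the plan says.** SAP 14.6.2.3 identifies users of non-randomized ESA by the reason recorded for the medication. One of the two qualifying reasons is "Non-randomized rhEPO treatment instead of study treatment during treatment period". The programming notes to Tables 1.029 and 1.030 also point to the recorded reason.

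For a single record, the end of use is "Duration (days) = earliest of (concomitant medication record end date, last non-zero dose date + 1 day"). From this the rule subtracts "latest of (concomitant medication start date, treatment start date) + 1 day", the last term being the usual inclusive-day correction. With several records, "then the duration of non-randomized ESA use will add the durations for all records", less overlapping days.

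SAP 6.2.5 says that "the duration of the non-randomized ESA use during the treatment period will be summarized" by arm with the usual statistics and in four categories: under 5, 5 to under 14, 14 to under 28, and 28 days or more.

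Other parts of the SAP handle similar records differently:

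- **Prior ESA (14.6.2.1):** "Stop date will be the concomitant medication record end date + gap factor". A one-time dose on or after the Week -4 visit gets 7 days.
- **Evaluable Hgb (14.6.3.1):** values count only if "not taken within the 8 weeks following a red blood cell transfusion, a whole blood transfusion, or a non-randomized ESA treatment".
- **On-treatment IV iron (14.6.3.2):** a record that starts after the on-treatment period has ended is given duration 0.

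**The concern.** Two features of the rule look wrong. First, a long-acting injection entered with the same start and end date counts as 1 day, although the SAP elsewhere extends ESA records across the dosing interval. Second, the cap is the last dose of active study treatment plus 1 day, while one selection reason is ESA given in place of study treatment. Protocol 7.2.4 allows for this during an interruption: in exceptional circumstances, "local standard of care for anemia management during this time may be considered based on consultation with the GSK medical monitor". If active treatment never resumes, such a record can start after its own cap.

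What is at stake is description. The primary estimand keeps Hgb values after non-randomized ESA. In a non-inferiority comparison with an ESA, a reader will want to know how long daprodustat participants received one. Tables 1.029 and 1.030 are the displays that report that length.

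**Working it through.** The plan states no figure for this derivation, so there is nothing to reproduce. The check applies the rule to test dates.

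**Inputs.** S and E are the record start and end, and T is treatment start. L is the last non-zero dose date, which SAP 14.6.1 defines as the last dose of active treatment. Gap factors come from SAP 14.6.2.1: 1.33 days (three times weekly), 6 (weekly), 13 (every 2 weeks), 27 (every 4 weeks). Dosing intervals come from Protocol 5.1: daprodustat three times weekly, epoetin alfa once or three times weekly.

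**Formula as written:** D = min(E, L + 1) − max(S, T) + 1.

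**1. One injection in mid-treatment.** With S = E = 100 and L = 360, D = 100 − 100 + 1 = 1 day for any agent. With the gap factor for the recorded frequency:

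- three times weekly: 1 + 1.33 = 2.33 days, still under 5
- weekly: 1 + 6 = 7 days
- every 2 weeks: 1 + 13 = 14 days
- every 4 weeks: 1 + 27 = 28 days

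A record entered as a one-time dose has no gap factor; the 14.6.2.1 rule gives it 7 days. All but the first case leave the lowest category.

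**2. Three every-4-weeks injections, days 100, 128 and 156.** As one record, D = 156 − 100 + 1 = 57 days. As three same-day records, D = 1 + 1 + 1 = 3 days. With the 27-day gap, both give 183 − 100 + 1 = 84 days. As written, the result depends on how the site entered the records.

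**3. ESA replaces study treatment, which is never resumed.** Let a 28-day course start k days after L. When it runs past the cap, D = (L + 1) − (L + k) + 1 = 2 − k.

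| k | D as written (days) |
|---|---|
| −1 | 3 |
| 0 | 2 |
| 1 | 1 |
| 2 | 0 |
| 3 | −1 |
| 7 | −5 |
| 14 | −12 |

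If the ESA takes the place of the next scheduled dose, k is 2 or 3 after three-times-weekly dosing (D = 0 or −1) and 7 after once-weekly epoetin (D = −5). Every value in the table falls in the under-5-days category.

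**4. The same course when study treatment resumes.** Days 202 to 229 with L = 360: D = 229 − 202 + 1 = 28 days.

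**5. Two records summed.** With L = 200, a record on days 100 to 113 gives 14 days. A course from day 207 gives 201 − 207 + 1 = −5. The total is 14 − 5 = 9 days, less than the first record alone.

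**6. Comparison with IV iron.** SAP 14.6.3.2 sets iron records starting after the on-treatment end to 0. SAP 14.6.2.3 has no such line for ESA.

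**The case against.** The strongest reply concerns selection. Tables 1.029 and 1.030 are titled as on-treatment, and SAP 14.4.1.5 ends the on-treatment phase for concomitant medication at last non-zero dose + 1 day. If that acts as a date filter, records starting at L + 2 or later never enter, and every remaining duration is at least 1 day. This stands as a possible reading. However, 14.6.2.3 and the table notes select by reason, and the SAP does not say which rule governs. Under a date filter, ESA recorded as replacing treatment after the final active dose would drop out of the table meant to show it.

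A second reply is that counting calendar days on record is a consistent convention. SAP 14.6.2.4 computes study-treatment exposure as stop minus start plus 1, the gap factors were built to standardize dose, and the 7-day one-time rule simply returns the dose given. This carries some weight: the 1-day count is a convention, not an arithmetic slip. But SAP 14.6.3.2 also uses gap factors to decide whether iron was in use at baseline and in each quarter, so within this SAP they are more than a dose device.

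A reader might also infer more than the documents support:

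- **That the efficacy conclusion is affected.** Neither the primary analysis nor the evaluable-Hgb analysis uses this variable.
- **That ESA use would go unseen.** The number and percentage of users is unaffected under reason-based selection. Table 2.013 shows evaluable-Hgb exclusions by visit, and Listing 1.014 gives ESA records.
- **That non-resumption always gives zero or less.** ESA starting by L + 1 gives a positive, though truncated, duration.
- **That any single long-acting injection should count as 28 days.** That needs a recorded every-4-weeks frequency.

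**Conclusion.** The point holds as a defect in a descriptive derivation. A same-day record counts as 1 day, against 7, 14 or 28 days under the SAP's own gap factors for weekly to every-4-weeks recording. A replacement record starting 2 or more days after the final active dose counts as 2 − k days, which is zero or negative, and reduces the participant's total when summed.

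The 1-day result assumes equal start and end dates on the record. The negative result assumes selection by reason alone and ESA starting after the cap. Once-weekly dosing occurs only with epoetin, so the distortion can differ between arms for the same event. The documents give no expected frequency of non-randomized ESA use, so the total understatement cannot be sized. It is confined to the duration statistics and categories in Tables 1.029 and 1.030. The correction is worth making because it is cheap and uses rules the SAP already contains.

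**What to change.** In SAP 14.6.2.3:

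1. State whether records are selected by reason, by date, or both, and align the titles of Tables 1.029 and 1.030 with that choice.
2. Extend each record end by the 14.6.2.1 gap factor for its recorded frequency, with 7 days for a one-time dose, before applying the cap. Count overlapping days once.
3. Set any record that starts after last non-zero dose + 1 day to 0, as 14.6.3.2 does for IV iron, so that no negative value is averaged or summed.
4. Report separately, by arm, the number and recorded days of records flagged as replacing study treatment that start or continue after last non-zero dose + 1 day.

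This needs no new data and a little more programming. Reported ESA durations will become somewhat longer.
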